5.1. Inclusion criteria

The following inclusion criteria apply:

1. Aged from 18 to 65 years
2. History of episodic or chronic migraine with or without aura meeting the diagnostic criteria listed in ICHD-III beta (2013) section 1, migraine, with the exception of "complicated migraine" (i.e., hemiplegic migraine, basilar-type migraine, ophthalmoplegic migraine, migrainous infarction)
3. Having a migraine attack lasting at least 3 hours
4. Migraine pain intensity stabilized for at least 1 hour
5. Frontal, retro-, or peri- orbital headache.

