- Since March 2015, an open-label pilot trial on the acute treatment of migraine using the Cefaly® device has been underway at Columbia University, NY. Patients experiencing a migraine attack for at least 3 hours (without use of acute medications during this time) and having stable pain intensity for at least 1 hour, are eligible to receive a 60-minute stimulation to treat their attack. Pain is assessed on a 10-point visual analogue scale (VAS) before, after the 1-hour treatment, and 2 hours after the beginning of the treatment. The study is still on-going, but the results to date confirm prior observations that e-TNS therapy via the Cefaly® device can significantly reduce pain intensity during an acute migraine attack, as measured via the VAS.

Based on the data from the above studies and preliminary findings from the open-label pilot trial at Columbia, it is reasonable to further investigate the efficacy of e-TNS with the Cefaly® device as an acute treatment for migraine via a double-blind, randomized, sham-controlled trial.

2. Study objective

The main objective of this study is to assess the efficacy of the Cefaly® device as an acute treatment of migraine attack in adult patients.

3. Study outcomes

Primary outcome:

- Mean change of pain score at 1 hour compared to baseline

Secondary outcomes:

- Proportion of patients not having required rescue medication at 2 hours
- Mean change of pain score at 2 hours compared to baseline (if rescue therapy was not used)
- Proportion of patients not having required rescue medication within 24 hours
- Mean change of pain score at 24 hours compared to baseline (if rescue therapy was not used)

4. Study design

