4.2.1. Recruitment phase

Two options are available to recruit patients:

- Eligible patients can be recruited during a standard care visit if they are experiencing a migraine attack having lasted at least 3 hours, with pain stabilized for at least 1 hour, and have not used acute migraine medication within the past 3 hours.
- Patients can also be screened beforehand (having been informed about the study at a standard visit or via advertisement), and arrange for an on-demand appointment when they are undergoing an attack for at least 3 hours, with pain stabilized for at least 1 hour.

Patient will receive the information and consent documents and have to sign these documents before study procedures are initiated. Then the investigator will verify that the patient meets all inclusion criteria and none of the exclusion criteria. If this is the case, the patient has to give a value on an 11-point visual analog scale (VAS) (0 = no pain, 10 = maximum pain) of the current pain associated with the migraine attack.

The patient will then be randomized to either the verum or the sham group. To this end, a unique device will be allocated to him/her.

The investigator will then apply the device on the patient and start the stimulation. If the patient cannot bear the paresthesia of the neurostimulation (needs to stabilize intensity before 4 minutes i.e. nociceptive threshold < 5 mA for impulse width of 250 μ s), the patient is considered meeting the exclusion criteria of allodynia (too low nociceptive threshold). The patient is in this case not included in the trial.

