8.2. Statistics

8.2.1. Sample size

Results from a randomized controlled trial on an acute migraine treatment (6) showed in the placebo group a reduction in mean pain score of 10% after 1 hour and 14% after 2 hours, compared to baseline. The results of the pilot trial on the acute treatment of migraine using the Cefaly® device showed a reduction in mean pain score of 59% after 1 hour and 55% after 2 hours. The standard deviation related to mean pain score was 2.42 after 1 hour and after 2 hours. Based on these results we could assume a difference in mean pain score of 2.83 after 1 hour and 2.40 after 2 hours between the active and placebo groups. A minimum of 17 patients in each group would be statistically required to detect a significant difference in mean pain score after 1 hour and after 2 hours, with a power of 80% and at two-sided alpha level of 5%, using a t-test for two independent samples.

A previous study reported 71% of patients from the placebo group using rescue medication compared to 41.33% for active groups on average (7). Considering these percentages, 43 patients in each group would have been statistically required to detect a significant difference in rescue medication use after 24 hours with a power of 80% and at two-sided alpha level of 5%, using a proportion test for two independent samples.

Overall, at least 43 patients in each group should allow to detect a significant difference between active and placebo groups in mean pain score after 1 hour and after 2 hours, and in rescue medication use. As the trial will be conducted in three different centres, the number of patients is rounded to 45 in each group (i.e. 15 patients per group and per centre). Consequently, 90 patients will be recruited.

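### No minimum baseline pain at entry: the primary 1-hour test is safe, but the 24-hour rescue comparison that sets the sample size has little slack to absorb patients with very low scores

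*Combined protocol and SAP*

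**What the plan says.** Section 5.1 puts three conditions on the attack to be treated: duration ("Having a migraine attack lasting at least 3 hours"), stability ("Migraine pain intensity stabilized for at least 1 hour") and a frontal or orbital location. None is a pain level, and no exclusion in section 5.2 concerns intensity. The diagnostic criteria in inclusion 2 describe the patient's migraine history, not the attack being treated.

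In section 4.2.1 the investigator first checks all inclusion and exclusion criteria. Only then does the rating follow: "If this is the case, the patient has to give a value on an 11-point visual analog scale (VAS", with anchors "0 = no pain, 10 = maximum pain". The score therefore screens nobody.

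The primary outcome in section 3 is "Mean change of pain score at 1 hour compared to baseline". In section 8.2.1 the sponsor writes "we could assume a difference in mean pain score of 2.83 after 1 hour and 2.40 after 2 hours", and sizes the trial on 24-hour rescue use of 71% against 41.33%. Section 8.2.2 describes no adjustment or stratification by baseline pain.

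**The concern.** A patient who enters at VAS 1 or 2 can fall by at most 1 or 2 points on either device. Such a patient adds little to a mean difference expressed in points and may have little reason to take rescue medication in either arm. If enough such patients enter, the pain estimate shrinks and becomes harder to interpret, because it mixes patients with substantial pain and patients near the floor of the scale. The contrast in rescue use also narrows. That comparison determined the number of patients, so it is the one most exposed. An entry rule cannot be repaired once patients are enrolled.

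**Working it through.** **Inputs from section 8.2.1.** Reductions in mean pain score: 59% (device) and 10% (placebo) at 1 hour, 55% and 14% at 2 hours. SD 2.42. Differences 2.83 and 2.40 points. Rescue use 71% and 41.33%. Two-sided 5%, 80% power, 45 per arm.

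**Assumptions not in the documents.** The share *f* of mild entrants, their mean VAS, and their rescue rate.

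**1. The plan's own figures.** A two-sample t-test (noncentral t) at SD 2.42 needs 13 per arm for 2.83 points and 17 per arm for 2.40, so the stated 17 comes from the 2-hour difference. For 71% against 41.33%, the pooled-variance formula without continuity correction gives 43 per arm, as stated. At 45 per arm, power is over 99.9% for 2.83 points and 82% for rescue.

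**2. Implied baseline.** Difference divided by the gap between percentage reductions: 2.83/(0.59 − 0.10) = 5.78 at 1 hour, and 2.40/(0.55 − 0.14) = 5.85 at 2 hours.

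**3. Contribution of a mild patient to the pain outcome.** Under the plan's percentages the expected between-arm difference is 0.49 × baseline: 0.49 points at VAS 1, 0.98 at VAS 2 and 1.47 at VAS 3.

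**4. Primary outcome with mild entrants at mean VAS 2.** Diluted difference = (1 − f) × 2.83 + f × 0.98.

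| f | 1-hour difference | Power, SD 2.42 | Power, SD widened for the baseline mix |
|---|---|---|---|
| 0% | 2.83 | >99.9% | >99.9% |
| 10% | 2.65 | 99.9% | 99.9% |
| 20% | 2.46 | 99.8% | 99.6% |
| 30% | 2.27 | 99.3% | 98.8% |

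With a mild mean of VAS 1 to 3 and f of 10-30%, the difference lies between 2.13 and 2.69 and power is at least 97%, even with the wider SD. At 45 per arm, 80% power is kept down to about 1.45 points.

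**5. Rescue outcome.** Sham rate = (1 − f) × 0.71 + f × s, where s is the sham rescue rate in mild patients. Device rate = (1 − f) × 0.4133 + f × s × k. Here k = 1 means no effect in mild patients, and k = 0.4133/0.71 = 0.582 is the plan's own relative risk. Power is the normal approximation for two proportions at 45 per arm.

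| f | No effect, s = 20% | Relative risk 0.582, s = 20% | Relative risk 0.582, s = 40% |
|---|---|---|---|
| 0% | 82% | 82% | 82% |
| 10% | 73% | 75% | 78% |
| 20% | 62% | 68% | 74% |
| 30% | 51% | 61% | 69% |

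Example, f = 20% and no effect: sham 0.8 × 0.71 + 0.2 × 0.20 = 0.608; device 0.8 × 0.4133 + 0.2 × 0.20 = 0.371; difference 23.7 points instead of 29.7; power 62%. In the no-effect column the choice of s between 10% and 30% moves power by about 1 point at most, and the number needed per arm rises from 43 to 54, 69 and 88-90.

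**The case against.** **The pain assumption may already include mild patients.** The background section describes an open-label pilot with much the same entry rules: an attack of at least 3 hours, stable for 1 hour, with no stated pain floor. If the 59% and 55% reductions in section 8.2.1 come from that pilot, as seems likely, then 2.83 points already reflects enrolment without a floor, and step 4 counts the dilution twice. The implied baseline near 5.8 also suggests that such enrolment does not fill with scores of 1 or 2. This stands as a possibility, although the background may not list every pilot criterion. It does not cover the rescue rates, which come from a different cited trial.

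**A reader might infer that the primary endpoint is underpowered, or that mild patients cannot show benefit.** The documents do not support either. The 1-hour test needs 13 per arm and has 45. The 2.83 points is a difference between group means, not a fall that each patient must show, and a patient at VAS 2 can show the assumed percentage reduction.

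**The rescue scenarios rest on assumptions.** The documents give neither the share of mild entrants nor rescue use by baseline pain. The no-effect column is the severe case. It also sits awkwardly beside a full proportional pain effect in the same patients, which is why the relative-risk columns are shown. The entry criteria of the trial that supplied the rescue rates are not described, so those rates cannot be said to apply only to moderate or severe pain.

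**Enrolment of very mild cases may be rare.** Criterion 3 requires a current migraine attack; admitting chronic migraine and medication overuse headache does not turn a background headache into an attack. Patients who ask for an on-demand appointment are probably in real pain. But section 4.2.1 also recruits at standard care visits, and no rule enforces a level.

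**Broad entry suits the stated objective,** which has no severity limit. That is a legitimate choice, but the plan neither gives it as a reason nor adjusts or sizes for it.

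**Conclusion.** The gap is real and its consequence is moderate. The entry rules admit patients near the floor of the scale, while the planning figures imply a mean baseline of about 5.8. For the primary outcome the effect is at most a smaller estimate (2.83 falling to 2.65, 2.46 or 2.27 points with 10%, 20% or 30% at mean VAS 2), and none of it if the pilot already included such patients. Power there stays at about 99%.

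The exposure lies with the 24-hour rescue comparison, a secondary outcome that nonetheless sets the trial size. It starts at 82%, and every scenario with 10% or more mild entrants takes it below the planned 80%: to 73-78% at 10%, 62-74% at 20% and 51-69% at 30%. These are sensitivity figures under assumed shares and rescue rates, not predictions. This is a cheap improvement to the design, not a flaw that undermines the trial.

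**What to change.** 1. Add to section 5.1 a minimum baseline VAS, at a level the sponsor chooses and justifies.
2. In section 4.2.1, move the existing VAS rating ahead of the eligibility check. It already precedes device allocation; with the new order a patient below the level is never allocated a single-use device.
3. In section 8.2.2, adjust the pain-change analysis for baseline VAS. This helps the pain outcomes but does not restore the rescue contrast.

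If the sponsor prefers to have no minimum, the protocol should say why, and the baseline adjustment becomes more important.

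Cost: one inclusion line, one reordered step and one analysis sentence, with no new measurement. Downsides: somewhat slower recruitment, a conclusion limited to attacks above the chosen level, and possible upward rounding of scores close to the threshold.

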5.2. Exclusion criteria

The following exclusion criteria apply:

1. Pregnant women
2. Patients having received Botox treatment in the prior 4 months
3. Patients having received supraorbital nerve blocks in the prior 4 months
4. Diagnosis of other primary or secondary headache disorders, except of Medication Overuse Headache
5. Patients with only temporal or occipital headache
6. Patients using opioid medication
7. Patients having taken abortive migraine medication in the prior 3 hours
8. Allodynia: intolerance to supraorbital neurostimulation (allodynia) that makes the treatment not applicable (the patients will be excluded if they are unable to tolerate the first 5 minutes of neurostimulation).
9. Implanted metal or electrical devices in the head
10. Cardiac pacemaker or implanted or wearable defibrillator
11. Patient having had a previous experience with Cefaly®

6. Medical device and treatment

6.1. Device description

The Cefaly® is a small, portable product, which is meant to be worn on the forehead by attachment to a self-adhesive electrode. Two 1.5V AAA batteries provide power to the Cefaly® device. The Cefaly® generates very precise electrical impulses that permit stimulation of the nerve fibers. The device acts by stimulation of the upper branch of the trigeminal nerve.

The device has been approved by the FDA as a class II therapeutic device indicated for the prophylactic treatment of episodic migraine in patients 18 years of age or older.

The Cefaly® device (Figure 2) is comprised of the following specifications:

- Dimensions: 163 mm x 170 mm x 40 mm.
- Weight: 30 g.

Figure 2 - Cefaly® device

The device is connected to the body via a self-adhesive electrode (Figure 3) applied on the forehead. The device specific for the trial will run sessions of 60 minutes. The Cefaly® electrode is 94 mm long and 30 mm high. It makes the interface between the device and the skin. This electrode has been approved by the FDA together with the device.

Figure 3 - Cefaly® electrode

6.2. Device technology

The Cefaly® is an external cranial neurostimulator designed for supraorbital neurostimulation (also known as external trigeminal nerve stimulation: e-TNS). Trigeminal nerve stimulation induces a sedative effect on the central nervous system (1).

The Cefaly® generates electrical impulses that are transmitted transcutaneously via a bipolar self-adhesive electrode placed on the forehead.

The Cefaly® operates on direct electrical energy, which is output from two 1.5V AAA batteries.

The Cefaly® delivers electrical energy in the form of rectangular biphasic pulses. The intensity is increasing linearly to reach a maximum of 16 mA after 14 minutes (and then stays constant for 46 minutes). The pulse frequency is 100 Hz. The pulse width is 250 μ s.

If the user feels that the intensity becomes too high, a simple pressure on the button will stabilize the intensity for the rest of the session.

The supraorbital electrode is designed in order to cover both sides of the supratrochlearis and supraorbitalis nerves, which are branches of the trigeminal nerve (Figure 4).

The electrical impulses generated by the Cefaly® device are transmitted transcutaneously via the supraorbital electrode to excite (trigger action potentials) the supratrochlearis and supraorbitalis nerves. Supratrochlearis and supraorbitalis (or supratrochlear and supraorbital) nerves belong to the upper branch of the trigeminal nerve (V1). Therefore the supraorbital neurostimulation is also known as external trigeminal nerve stimulation.

[figure not shown]

Figure 4 - The electrode placed on the forehead covers the supratrochlearis and supraorbitalis nerves

6.3. Mechanism of action

The Cefaly® device generates electrical impulses. Electrical impulses get out of the device via 2 metallic contacts. Contacts are in connection with 2 conductive areas on the self-adhesive electrode. The self-adhesive electrode is applied on the forehead. Therefore electrical impulses generated by the Cefaly® device are running through the metallic contacts then through the electrode in order to carry out excitation on the nerve fibers just located under the forehead skin i.e. supratrochlearis and supraorbitalis (or supratrochlear and supraorbital) nerves which belong to the trigeminal nerve. Consequently electrical impulses generated by the Cefaly® trigger signals (action potentials) on supratrochlear and supraorbital nerves or trigeminal nerve. Repetitive excitation of trigeminal nerve is a neuromodulation of the trigeminal system. Neuromodulation of the trigeminal system induces a sedative effect on the central nervous system and a trigeminal nociceptive threshold modification.

6.4. Use during the trial

The investigator will apply the device on the patient's head. A session of 60 minutes will be applied. If the patient experiences discomfort during the stimulation, he or she can stabilize the intensity of stimulation at any time by pushing the "on" button of the device (the current intensity will then remain stable until the end of the session). The patient should at least let the device increases the intensity for 4 minutes in order to be included in the trial: before this point, the patient's nociceptive threshold is considered too low because of allodynia.

6.5. Sham device

As this study is sham-controlled, a sham neurostimulator has to be provided. The sham stimulator is identical in shape and colour as the verum Cefaly® device. Also, it will beep and flash identically to the verum Cefaly® device. No difference will exist between the sham and verum devices and it won't be possible for the patient as for the investigator to know which device is verum or sham.

The only difference will be in the stimulation parameters. The sham stimulator will contain a stimulation program with a low frequency, which will be sufficient for the patient to feel paresthesia similar to that produced by the verum, but will not induce a sedative effect to the central nervous system.

The sham device has been validated in a clinical trial on 128 subjects (62 verum and 66 sham). Following the trial, the patients were indeed unable to distinguish whether they received an active or a sham device.

6.6. Medication during the trial

No medication can be used during the 2 hours of the study (1 hour of Cefaly stimulation followed by 1 hour of observation). Any rescue medication can be used after these 2 hours and have to be recorded during the 24 hours following the beginning of the treatment.

If a patient wants a rescue medication during the one-hour treatment phase it is a drop-out, if the patient wants a rescue medication after the one-hour treatment phase but before the 2 hours of the study the last value carried-forward is applied.

6.7. Device provisioning

The promoter will deliver the specific devices directly to the investigators. The devices will be delivered by sets of even number of verum and sham devices, ensuring at least one device per patient. The investigator will not be able to distinguish both. A single device cannot be reused on different patients. Each device will bear a unique number that has to be reported in the patient's CRF and will allow to identify, at the end of the study, whether the patient used a sham or verum device. Electrodes will be delivered in enough quantity to ensure to have one per patient.

7. Practical study modalities

7.1. Measures

Pain score. In order to evaluate the modification of pain score from baseline to 1-hour treatment and to 2-hour treatment, patients will be asked to give an indication on the pain level using a visual analogue scale (VAS) counting eleven levels (0 = no pain, 10 = maximum pain) at the recruitment phase (before applying the treatment), right after the treatment phase (1 hour), 2 hours after the beginning of the treatment and at 24 hours after the beginning of the treatment.

Rescue medication after the treatment. The investigator will also record whether the patient uses another acute medication right after the 2 hours. Patients will also be contacted 24 hours after the beginning of the treatment to report whether or not rescue medication was taken within the 24 hours following the beginning of the treatment.

The following table depicts when the different measures will be made:

	Baseline	1 hour	2 hours	24 hours
Pain score	●	●	●	●
Rescue medication intake			●	●

7.2. Calendar

The study is foreseen to start in December 2016 and to be finished by July 2016.

7.3. Blinding

Blinding between verum and sham devices has been previously validated in a trial on 128 patients (62 verum and 66 sham). A new device will be used for each study patient. Sham and verum stimulators and electrodes will look alike. Verum will use a high frequency impulse and sham a low frequency. Both devices will generate paresthesia on the forehead to ensure blinding. Patients will therefore not be able to know if it is the active neurostimulation or the sham.

The investigator and research coordinator will be blinded from which device the patient has (sham or verum). A built-in electronic system will record the treatment delivered to each patient.

The treatment allocation will be concealed using the following procedure. Verum and sham stimulators will be programmed by the manufacturer Cefaly Technology. They will be sent to each investigator by blocks with equal number of verum and sham devices. The only indication on the device box will be a

number. The list of correspondence will be sent in a sealed envelope to the investigators. This procedure ensures a blinding from the enrolling investigator as well.

8. Data management and statistics

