8.1. Data management

The data will be included in the case report form (CRF) that will be provided by the investigator to the promoter anonymously, using a numbering system. To trace to which group the patient belongs (sham or verum), the device number will be collected in the CRF as well.

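### Section 7.3 leaves the verum/sham key, in a sealed envelope, with the investigators who must stay blinded, and nothing requires the analysis sets to be fixed before devices are decoded

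*Combined protocol and SAP*

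**What the plan says.** **Key and site staff (section 7.3).** The investigator and the research coordinator are to be blinded. Of the devices, the section says "Verum and sham stimulators will be programmed by the manufacturer Cefaly Technology". They go to the sites in blocks balanced between verum and sham, in boxes marked only with a number. On the key it says "The list of correspondence will be sent in a sealed envelope to the investigators", and it concludes: "This procedure ensures a blinding from the enrolling investigator as well".

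**Devices and decoding (section 6.7).** "The promoter will deliver the specific devices directly to the investigators". The device number is written in the CRF and "will allow to identify, at the end of the study, whether the patient used a sham or verum device".

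**Data flow (section 8.1).** The CRF is "provided by the investigator to the promoter anonymously, using a numbering system". The section adds: "To trace to which group the patient belongs (sham or verum), the device number will be collected in the CRF as well".

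**What is not stated.** The sections on blinding, data management, statistics and adverse events do not say:
- who may open the envelope, or when;
- how the seal is checked, or whether the envelope is returned;
- whether the list covers a block of devices, a site or the whole trial;
- whether an independent person holds a copy;
- whether the promoter, data manager or analyst is blinded;
- whether the database is locked before device numbers are decoded.

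**The concern.** The key is placed with the people it must be kept from, and that placement is then cited as part of what blinds them. A list differs from a single code: decoding one patient shows every other device on the same list, including those still waiting to be used. Concealment of future allocations would be lost along with blinding of past ones.

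The matter is more than formal because site staff have decisions to make after a device has been allocated. They apply the tolerance step, they deal with stimulation that stops early, and they collect a self-rated 0 to 10 pain score that is the primary outcome. The first two bear on who is analysed. Knowledge of the arm could influence each of them.

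The promoter side raises a smaller question. Device numbers arrive with outcomes, and the plan does not say that analysis decisions must be final before anyone links those numbers to an arm.

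**Working it through.** The plan gives no figure for this point, so the check is a count of exposed patients followed by a reading of the sections in the order in which decisions fall.

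**1. Exposure if one list is opened**

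Inputs: 90 patients (sections 5 and 8.2.1); three centres with 15 patients per group per centre (section 8.2.1); four sites (section 4.1). The centre counts disagree, so both are used. The plan's total reproduces: 15 x 2 x 3 = 90. Equal recruitment across sites is assumed for four sites.

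- List covers one of three centres: 90/3 = 30 patients, 30/90 = 33%.
- List covers one of four sites: 90/4 = 22.5, so 22 or 23 patients, 22.5/90 = 25%.
- List covers the trial: 90/90 = 100%.
- List covers one shipped block: not computable, because the block size is not given.
- Single-device envelope, for comparison: 1/90 = 1.1%.

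**2. What knowledge of the arm could touch**

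- *Next patient.* Unused devices on an opened list are known before enrolment.
- *Tolerance step.* Section 4.2.1 allocates the device, starts stimulation, and then does not include patients who cannot bear it. Sections 4.2.1 and 6.4 set the limit at 4 minutes; exclusion criterion 8 in section 5.2 refers to the first 5 minutes. These need to be reconciled, and until they are, there is room for judgement. The step comes well before the 1-hour score, so it cannot select on 1-hour response.
- *Early stops.* Section 4.2.4 counts an accidental device stop as a drop-out but keeps a patient who chooses to stop and remains available. Section 4.2.2 says the device records duration, intensity and interruption, but not that the record separates the two causes. Section 8.2.2 defines the analysis set by more than 4 minutes of use, no rescue medication before 1 hour, and a reported 1-hour score. It does not mention accidental stops, so whether such a patient is analysed depends on which section is followed.
- *Pain score.* Section 7.1 uses a self-rated 11-level scale, collected at the site at baseline, 1 hour and 2 hours.

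**3. Promoter side**

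Section 8.1 gives the promoter device number and outcomes together. The key originates where the devices are programmed, with the manufacturer. Section 6.7 puts identification at the end of the study, but does not say whether that means after database lock or after the analysis sets are settled.

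**4. Effect on the result**

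The documents give no probability of opening, no rate of tolerance failures or accidental stops, and no outcome distribution among such patients. A bias in the mean pain difference therefore cannot be calculated. The planned sample sizes (17, 43 and 45 per group) do not depend on this point.

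**The case against.** The strongest reply is that a sealed envelope does its job until somebody opens it. Nothing in the text permits opening during the trial. Section 6.7 places decoding at the end of the study, and section 9 describes no code break, so a serious adverse event as the trigger is only a possibility. Site staff are also protected by devices that look, beep and flash alike and by number-only boxes. Patient blinding rests on the sham design: felt paresthesia in both arms and a cited earlier validation in 128 subjects (sections 6.5 and 7.3). The patient, not the investigator, presses the button, and the device keeps a log. The main rules for drop-outs and the analysis set are written in advance. Single-device envelopes would themselves rely on seals.

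All of this stands, and it rules out several stronger readings that a reader might infer:

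- *That the whole blind hangs on one envelope per site holding a full list.* The text states neither the number of envelopes nor the scope of the list, and patient blinding does not depend on it.
- *That the procedure fails to blind investigators.* It blinds them while the seal holds; the weakness is the lack of control over the seal and the amount revealed if it breaks.
- *That the sponsor side is unblinded contrary to the plan.* The plan claims blinding for patient, investigator and coordinator only. It does not say that promoter and manufacturer are one party, or that those handling data hold the key.
- *That a definite inflation of the treatment effect follows.* Any such figure needs an assumed share of selectively removed patients, for which the documents give no source.

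What the reply does not meet is the choice of where to keep the key. Look-alike devices give no protection against a readable list, and the plan gives no reason why enrolling sites need one.

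**Conclusion.** The concern holds in a limited form. Section 7.3 keeps the allocation key with the staff who must not know it and counts this toward their blinding, without an opening rule or accounting for the envelope. This is a stated procedure with a better and cheap alternative, so it is more than a missing detail.

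The size is an exposure, not a bias. One opening would reveal 22 to 30 of 90 patients (25% to 33%) if the list covers a site, and all 90 if it covers the trial. The range rests on an assumed list scope, on equal recruitment for the four-site figure, and on the unresolved count of three centres or four sites. Nothing in the documents suggests that an envelope would in fact be opened.

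The absence of a lock before device numbers are linked to arms is a second, separate gap. It matters mainly because the classification of early stops is not fully settled by the written rules. The change should be made, but the point does not undermine the design or the sample size.

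**What to change.** - **Section 7.3:** do not send the list to enrolling sites. Keep it with a named person who has no role in enrolment, data review or analysis.
- **Section 7.3, if a site-level code break is wanted:** supply individually sealed, opaque envelopes, one per device, and account for every one at the end. An opening then reveals one patient.
- **Section 8.1:** state that the database, the drop-out classification and the analysis sets are locked before device numbers are linked to verum or sham, and say who makes the link.

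The cost is naming a list holder, a few sentences in 7.3 and 8.1, and, if code breaks are kept, about 90 envelopes with an accountability log. The downside is minor administration. The number of patients, the measurements and the planned tests stay as they are.
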